3.2. Secondary Objectives

- to study if early intervention with sargramostim is safe (number of AEs/SAEs)
- to study if early intervention with inhaled sargramostim affects clinical outcome defined by
 Duration of hospital stay
 Mean and median change in 6-point ordinal scale between day 1 and day 6
 Mean and median change in clinical sign score between day 1 and day 6
 Time to clinical sign score <6 maintained for 24h
 Mean and median change of SOFA score between day 1 and day 6 or between day 1 and day 10.
 Mean and median change NEWS2 score between day 1 and day 6 or between day 1 and day 10.
 Time to NEWS2 score less than 2 for at least 24h
- to study if early intervention with sargramostim affects the rate of nosocomial infection
- to study if early intervention with inhaled sargramostim affects progression to mechanical ventilation and/or ARDS
- to study if treatment with sargramostim affects all cause mortality rate at 28 days and 20 weeks post inclusion
- to study if treatment with sargramostim affects features of secondary haemophagocytic lymphohistiocytosis, as defined by Hs score (temp, organomegaly, cytopenia, triglycerides, fibrinogen, ferritin, AST and known immunosuppression)
- to study if treatment with sargramostim has a favourable effect on long term 10-20 week follow up

4. End Points + Time Points

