4.2. Secondary End Points + Time Points

- to study if early intervention with sargramostim is safe (number of AEs/SAEs)

Although sargramostim has been given previously by inhalation to patients with ARDS and interstitial lung disease, data on safety in patients with COVID-19 infection are currently lacking. Since we are randomizing against 5 days of no sargramostim treatment, comparison of AEs and SAEs between group A and group B will be very informative.

-to study if early intervention with inhaled sargramostim affects clinical outcome defined by Length of hospital stay

Mean and median change in 6-point ordinal scale change between day 1, day 6

Mean and median change in clinical sign score between day 1 and day 6

Time to clinical sign score <6 maintained for 24h

Mean and median change of SOFA score between day 1 and day 6 or between day 1 and day 10.

Mean and median change NEWS2 score between day 1 and day 6 or between day 1 and day 10.

Time to NEWS2 score less than 2 for at least 24h

- to study if early intervention with sargramostim affects the rate of nosocomial infection

Patients with viral respiratory infection are at risk of secondary bacterial infections. As part of routine clinical care, sputum samples will be collected in patients suspected of secondary bacterial pneumonia, and checked for the presence of bacteria.

-to study if early intervention with inhaled sargramostim affects progression to mechanical ventilation and/or ARDS

Decreasing oxygenation often leads to the need for non-invasive or invasive mechanical ventilation, and if severe enough to a diagnosis of ARDS. We will therefore as a secondary endpoint also study if early intervention with inhaled sargramostim prevents progression to criteria-defined ARDS (according to the American-European Consensus Conference (AECC) diagnostic criteria for ARDS: acute onset; ratio of partial pressure of arterial oxygen to fraction of inspired oxygen (PaO_2/FiO_2) of 200 or less, regardless of positive end-expiratory pressure; bilateral infiltrates seen on frontal chest radiograph; and pulmonary artery wedge pressure of 18 mm Hg or less when measured, or no clinical evidence of left atrial hypertension), requiring high-flow oxygen devices, non-invasive mechanical ventilation, mechanical ventilation, by measuring the day from admission when this diagnosis is made or therapies are initiated.

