9.4. Schematic overview of the data collection & interventions

10. Procedure	Screening	D1	D2-D5	D6/discharge	D7-D9	D10	Follow-up (10-20 weeks after D1)
Informed consent	X						
Inclusion/exclusion criteria	X						
Randomization		X					
Medical history & biometry	X						
Anamnesis and (S)AE inquiry	X						X
Concomitant medication	X						X
Physical examination ^l	X						X
6 Minutes Walk Test ^{o, i}							X
Vital signs ^a	X						X
ECG ^l				On clinical grounds			
Chest X-ray and/or (HR)CT scan				On clinical grounds			X ^m
Lung function ^l							X
Routine laboratory assessments^l on clinical grounds, except:	X	X ^b		X ^c			X ^c
- screening/day 1 and day 6/discharge							
Serum pregnancy test	X						
Study blood sampling							
- 5 ml serum tube		X		X			X
- 10 ml EDTA tube (selected centers only)							
Arterial blood gas^d		X		X			X
Score assessments							
- 6-point ordinal scale ^e							X
- Clinical sign score ^f							X
- NEWS2 score ^g							X
- SOFA score ^h		X		X		X	X
- HScore ⁱ		X		X			X
- CURB-65 ^j		X					

SARPAC

- APACHE II ^k		X					
- Glasgow Coma Scale	→						X
- HRCT fibrosis score ^m							X
IMP ⁿ		(X)	(X)	(X)	(X)	(X)	
Drug compliance		→					

^a Includes morning assessment (7-10 am) of T°C (actual and highest last 24h), Pulse rate, Blood Pressure, Respiratory Rate, SpO2 by pulseoximetry. Time point assessment (7-10 am) is not applicable for the Follow-Up visit.

^b Should minimally include haemoglobin, platelets, WBC count, eosinophils, lymphocytes, CD4 and CD8 T cell count, CRP, bilirubin, AST, ALT, LDH, creatinine, fibrinogen, triglycerides, ferritin, ureum, troponin, D-dimers.

^c Should minimally include haemoglobin, hematocrit, platelets, WBC count, neutrophils, eosinophils, lymphocytes, CD4 and CD8 T cell count, CRP, bilirubin, AST, ALT, LDH, creatinine, fibrinogen, triglyceride, ferritin, troponin, D-dimers, ESR, CK

^d Patient sitting upright breathing room air for a minimum of 3 minutes. If this is impossible due to dependency to supplemental oxygen, FiO2, oxygen flow rate, and method of oxygen delivery should be noted in the patient file. If arterial blood gas is taken within 24h before first dose administration, the arterial blood gas of screening can be used as D1 value.

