^e Defined as 1 = Death; 2 = Hospitalized, on invasive mechanical ventilation or ECMO; 3 = Hospitalized, on non-invasive ventilation or high flow oxygen devices; 4 = Hospitalized, requiring supplemental oxygen; 5 = Hospitalized, not requiring supplemental oxygen; 6 = Not hospitalized.

^f (0-18) by scoring 6 clinical signs from 0 to 3 (0 = absent, 1 = mild, 2 = moderate and 3 = severe): Fever (0 = <37°C; 1 = 37.1-38°C; 2 = 38.1-39°C; 3 = >39°C) last 24h; Cough; Fatigue; Shortness of breath; Diarrhea; Body pain.

^g NEWS2 (see <https://www.mdcalc.com/national-early-warning-score-news-2>): requires RR, SpO2, T°C, SBP and pulse.

^h SOFA score (see <https://www.mdcalc.com/sequential-organ-failure-assessment-sofa-score>): requires PaO2, FiO2, platelet count, GCS, bilirubin, MAP and creatinine.

ⁱ HScore (see <https://www.mdcalc.com/hscore-reactive-hemophagocytic-syndrome>): requires T°C, haemoglobin, WBC count, platelets, ferritin, triglycerides and AST (BM aspirate is not required).

^j CURB-65 (see <https://www.mdcalc.com/curb-65-score-pneumonia-severity>): requires confusion, BUN, RR, blood pressure and age.

^k APACHE II (see <https://www.mdcalc.com/apache-ii-score>): requires age, T°C, MAP, pH, pulse, RR, sodium, potassium, hematocrit, creatinine, WBC count, GCS and FiO2.

^l Intervention is standard of care and is being performed regardless of inclusion in the study.

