12.1. Sample size calculation

The outcome(s) on which the sample size calculation is based upon, is the primary endpoint measurement of oxygenation, defined as ratio of $\text{PaO}_2/\text{FiO}_2$ and P(A-a)O_2 .

Sample calculation and power analysis have been performed using Genstat. The target difference is the difference measured at the primary endpoint (at day 6) between the control and the treated group. Given a sample size of 40 patients each, a minimal improvement of 10% in the treated group relative to the control group will be detected as significant at a significance level of 0,01 with a power of 0.90. The error variance was set at 100 units, corresponding with a standard deviation of 10 units.

The post-treatment evaluations should be assessed within 24 hours of the last dose of treatment. That is, Day 6 will be the timepoint for measures of efficacy endpoints based on 5 days of treatment, and Day 10 for patients who complete 10 days of treatment. If the patient is discharged from hospital prior to the day 6 (or day 10) efficacy evaluations, the values at day of discharge will be used as value for measuring efficacy endpoints.

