Comparison will be between active group A receiving sargramostim on top of standard of care and control group B receiving standard of care. The change from baseline and daily change from baseline in oxygenation/respiratory parameter of P(A-a)O_2 gradient, ratio of $\text{PaO}_2/\text{FiO}_2$ and ratio of $\text{SpO}_2/\text{FiO}_2$ will be evaluated and summarized between group A and group B at Day 6. The difference of change from baseline between two groups will be tested by a t-test. In general, the last observed measurement prior to the first dose of study treatment occurred on Day 1 visit will be considered the baseline measurement. Day 6 is the primary analysis point. If the patient leaves hospital prior to the day 6 analysis point, oxygenation at day of discharge will be used as value for measuring primary endpoint.

The analyses described above will also be performed between group A (early 5 day intervention with sargramostim) and group D (late 5 day intervention with sargramostim). Change from baseline (D1) to Day 10, daily change from baseline (D1) at Day 10 in oxygenation/respiratory parameter of P(A-a)O_2

gradient, ratio of $\text{PaO}_2/\text{FiO}_2$ and ratio of $\text{SpO}_2/\text{FiO}_2$ will be summarized as well. A t-test will be conducted to compare the difference between the groups.

The same analyses will be repeated for pathological oxygenation parameter of P(A-a)O_2 gradient, ratio of $\text{PaO}_2/\text{FiO}_2$ and ratio of $\text{SpO}_2/\text{FiO}_2$ including summary of their value and change from baseline at Day 6 and Day 10. A waterfall plot will be used to represent the change from baseline and percentage change from baseline on Day 6 for 1) oxygenation parameter of P(A-a)O_2 gradient; 2) pathological oxygenation parameter of P(A-a)O_2 gradient; 3) ratio of $\text{PaO}_2/\text{FiO}_2$; 4) ratio of $\text{SpO}_2/\text{FiO}_2$. Percentage change from baseline of P(A-a)O_2 gradient and ratio of $\text{PaO}_2/\text{FiO}_2$ on Day 6 and follow-up will be summarized.

Reasons of missing AA gradient values on Day 6 will also be summarized.

The normal value of AA gradient for room air is calculated as: $2.5 + (0.21 \times \text{Age})$. All the results including change from baseline, and maximum change from baseline after 5 day intervention with sargramostim, normal AA gradient value for room air and flag of abnormality on Day 6 will be listed.

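### Section 12.1 applies the discharge-day value to the 6-point ordinal scale, where it can under-score patients who have gone home and miss death or readmission before Day 6

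*Protocol*

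**What the plan says.** The discharge rule appears in two widths. Sections 4.1, 5.1, 7.1.2 and 12.2 of the protocol confine it to oxygenation or the primary endpoint; in 12.2 the wording is "oxygenation at day of discharge will be used as value for measuring primary endpoint". The closing sentence of section 12.1 is broader. For discharge before the Day 6 or Day 10 efficacy evaluations, "the values at day of discharge will be used as value for measuring efficacy endpoints", and no endpoint is excepted.

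The 6-point scale is one of those endpoints. Section 3.2 lists it under clinical outcome as "Mean and median change in 6-point ordinal scale between day 1 and day 6", and section 4.2 repeats it. The footnote to the schedule in section 9.4 defines the categories: 1 is death, 2 to 5 all describe patients in hospital, and the top of the scale reads "5 = Hospitalized, not requiring supplemental oxygen; 6 = Not hospitalized".

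The protocol does not say whether the score for the day of discharge is the one made on the ward or the patient's status after leaving. The 7-10 am window in section 9.4 belongs to the vital-signs footnote, not to this scale.

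**The concern.** Carrying the last value forward is defensible for a blood gas, which cannot be taken once the patient is at home. The ordinal scale is different. It records location and level of support, discharge itself defines its best category, and status on Day 6 can be established without a visit.

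Applied to this scale, the rule has two consequences:

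- If the ward score is carried, a patient who goes home on Day 3 ties with one still in bed on Day 6 without oxygen. That shrinks a favourable difference between arms.
- Whichever score is carried, events between discharge and Day 6 are ignored, although the scale has a category for death and categories for renewed hospital care.

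The trial is also open-label. If the text allows either 5 or 6 for the same patient, sites can score identical cases differently with the allocation known.

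**Working it through.** **Step 1: reach of the rule.** The change on the 6-point scale from Day 1 to Day 6 is a listed clinical-outcome endpoint (3.2, 4.2). Section 12.1 covers efficacy endpoints without exception, so the rule reaches it. The four narrower statements do not mention the scale and do not cancel the broader sentence.

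**Step 2: scores under each reading.**

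| Patient | Status on Day 6 | Ward score carried | Post-departure score carried |
|---|---|---|---|
| Discharged Day 3 off oxygen, well on Day 6 | 6 | 5 | 6 |
| Discharged Day 3 on oxygen, well on Day 6 | 6 | 4 | 6 |
| Discharged Day 3, died Day 5 | 1 | 5 or 4 | 6 |
| Discharged Day 3, readmitted by Day 6 | 2 to 5 | 5 or 4 | 6 |

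For a patient who starts in category 4 and goes home off oxygen, the ward reading credits 5 − 4 = 1 step instead of 6 − 4 = 2. If the patient is still on oxygen at discharge it credits 0.

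**Step 3: size on the ward reading.** The protocol gives no power figure for this endpoint; the power statement in 12.1 concerns oxygenation and does not bear on the point. Nor does it give discharge rates or an ordinal distribution, so everything below except the 40 per arm is an assumption.

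Let dC and dA be the proportions discharged before Day 6 in the control and active arms, m the mean score of those still in hospital (taken as equal in both arms), and s the score given to discharged patients. With equal baselines, the difference in mean change is (dA − dC) × (s − m).

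Assume those still in hospital fall 8/12/50/30% into categories 2 to 5. Then m = 0.16 + 0.36 + 2.00 + 1.50 = 4.02. Actual status gives s = 6. The rule gives s = 5 if all leave off oxygen, and s = 0.7 × 5 + 0.3 × 4 = 4.7 if 30% leave on oxygen.

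| Discharged, control v active | Actual status (s = 6) | Rule, all 5 | Rule, 70% at 5 and 30% at 4 |
|---|---|---|---|
| 10% v 25% | 0.15 × 1.98 = 0.297 | 0.15 × 0.98 = 0.147 | 0.15 × 0.68 = 0.102 |
| 20% v 40% | 0.20 × 1.98 = 0.396 | 0.20 × 0.98 = 0.196 | 0.20 × 0.68 = 0.136 |
| 30% v 55% | 0.25 × 1.98 = 0.495 | 0.25 × 0.98 = 0.245 | 0.25 × 0.68 = 0.170 |

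The share of the effect retained is 0.98/1.98 = 49%, or 0.68/1.98 = 34%, whatever the discharge rates.

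Simulation of 4,000 trials with 40 per arm and a two-sided Mann-Whitney test at 0.05 (chosen for illustration; the protocol names no test for this scale) gave power of about 0.22, 0.36 and 0.54 down the rows with actual status. With all at 5 it was 0.13, 0.22 and 0.35. With the 70/30 split it was 0.09, 0.11 and 0.16.

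**Step 4: sensitivity.** Take instead 3/10/15/42/30% over categories 1 to 5. Then m = 0.03 + 0.20 + 0.45 + 1.68 + 1.50 = 3.86. At 20% v 40% discharged the difference is 0.20 × 2.14 = 0.428 against 0.20 × 1.14 = 0.228. At 25% v 50% it is 0.25 × 2.14 = 0.535 against 0.25 × 1.14 = 0.285. The share retained is 1.14/2.14 = 53%, so the pattern is the same.

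**The case against.** The strongest reply is that the protocol never says the discharge-day score is taken before departure. A patient who has left by the evening meets "6 = Not hospitalized" that same day, and nothing forbids recording it. That is correct. A reader might infer that category 6 cannot be reached under the rule; the text does not support that as a certainty. It follows only on the ward reading, and discharge on Day 6 itself might be an exception even then. The alternative reading still leaves the score unfixed between 5 and 6, and does nothing for death or readmission.

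A reader might also infer that the benefit of early discharge is lost. It is not. A move from 4 to 5 still counts, so the effect shrinks without vanishing, and hospital stay is a separate secondary endpoint (3.2, 4.2). Deaths after discharge are not lost to the trial either: section 12.2 collects survival to 20 weeks and plans Day 28 risks and a Cox model. These safeguards limit the damage, but they do not correct a mis-scored ordinal endpoint.

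Third, the broad sentence occurs once, in a section about sample size for oxygenation, and the SAP mentioned in 12.2 was not available and may settle the scoring. That would be a good answer to an omission. Here the protocol states a rule, and the rule is unsuited to this scale.

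Finally, the magnitudes are hypothetical, the scale is unpowered even when scored on actual status, and the window for death or readmission after discharge is only a few days. All of that stands, and it keeps the point modest.

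**Conclusion.** The point holds in limited form. By its wording, section 12.1 extends an oxygenation rule to the 6-point scale. If the ward score is what is carried, patients discharged before Day 6 are scored at least one category below their Day 6 status, provided they remain alive and out of hospital. The early-discharge effect on this scale then falls by about half, or by about two thirds if 30% leave on oxygen. Those fractions rest on assumed in-hospital distributions that are equal in both arms. On either reading, death or readmission before Day 6 leaves a favourable score in place; the documents give no basis for saying how often that would happen.

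The primary oxygenation endpoint is not touched by this point, and length of stay and mortality are analysed separately. This is a correction worth making to one secondary endpoint, not a threat to the trial's main comparison.

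**What to change.** In section 12.1, limit the discharge-day substitution to measured values: blood gases, SpO2/FiO2, and scores that need an examination (SOFA, NEWS2, clinical sign score). Add to sections 12.1 and 4.2, and mirror in the SAP, that the 6-point scale is scored on actual status on the analysis day: alive and out of hospital = 6, dead = 1, readmitted = the category that then applies. This uses the section 9.4 definitions as they stand and removes the ambiguity about when on the discharge day the score is taken.

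The cost is a sentence or two and perhaps one eCRF item. Survival is already collected (12.2), but the data list in section 9.3 names the day of admission and no readmission field. Safety reporting would not reliably fill the gap: hospitalisation is a seriousness criterion (14.1), but section 14.5 excludes progression to respiratory failure or ARDS from adverse-event reporting. An explicit item for readmission by Day 6, with the level of respiratory support, would close it.

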12.2. Type of statistical methods

All endpoints will be summarized and where relevant represented graphically

A detailed statistical analysis plan (SAP) has been set up by EffectStats LLC, Cambridge Massachusetts, USA. The statistical tests to be used to look at improvements in oxygenation between treatment groups will be a Chi-square test. Mortality frequencies will be analyzed using Wald test.

Key timepoints of interest for endpoints include Day 6 and Day 11, where data are available. All available efficacy data will be tabulated and presented for all patients in the mITT Population.

Oxygenation after 5 days of Sargramostim Intervention

To measure the effectiveness of sargramostim on restoring lung homeostasis, the primary endpoint of this intervention is measuring oxygenation after 5 days of inhaled (and intravenous) treatment through assessment of pretreatment and post-treatment ratio of $\text{PaO}_2/\text{FiO}_2$, $\text{SpO}_2/\text{FiO}_2$ and through measurement of the P(A-a)O_2 gradient. During the 5 day treatment period, daily measurements of oxygen saturation (pulse oximetry) in relation to FiO_2 will be performed. Negative value of P(A-a)O_2 gradient would be removed from the primary analysis.

P(A-a)O_2 gradient, $\text{PaO}_2/\text{FiO}_2$ ratio and $\text{SpO}_2/\text{FiO}_2$ are defined as:

$\text{P(A-a)O}_2 \text{ gradient} = [(\text{FiO}_2) \times (\text{Atmospheric Pressure} - \text{H}_2\text{O Pressure}) - (\text{PaCO}_2/0.8)] - \text{PaO}_2$

$\text{PaO}_2/\text{FiO}_2 = \text{Partial Pressure Oxygen/Fraction of Inspired Oxygen} \times 100$

$\text{SpO}_2/\text{FiO}_2 = \text{Oxygen Saturation/ Fraction of Inspired Oxygen} \times 100$

Comparison will be between active group A receiving sargramostim on top of standard of care and control group B receiving standard of care. The change from baseline and daily change from baseline in oxygenation/respiratory parameter of P(A-a)O_2 gradient, ratio of $\text{PaO}_2/\text{FiO}_2$ and ratio of $\text{SpO}_2/\text{FiO}_2$ will be evaluated and summarized between group A and group B at Day 6. The difference of change from baseline between two groups will be tested by a t-test. In general, the last observed measurement prior to the first dose of study treatment occurred on Day 1 visit will be considered the baseline measurement. Day 6 is the primary analysis point. If the patient leaves hospital prior to the day 6 analysis point, oxygenation at day of discharge will be used as value for measuring primary endpoint.

The analyses described above will also be performed between group A (early 5 day intervention with sargramostim) and group D (late 5 day intervention with sargramostim). Change from baseline (D1) to Day 10, daily change from baseline (D1) at Day 10 in oxygenation/respiratory parameter of P(A-a)O_2

gradient, ratio of $\text{PaO}_2/\text{FiO}_2$ and ratio of $\text{SpO}_2/\text{FiO}_2$ will be summarized as well. A t-test will be conducted to compare the difference between the groups.

The same analyses will be repeated for pathological oxygenation parameter of P(A-a)O_2 gradient, ratio of $\text{PaO}_2/\text{FiO}_2$ and ratio of $\text{SpO}_2/\text{FiO}_2$ including summary of their value and change from baseline at Day 6 and Day 10. A waterfall plot will be used to represent the change from baseline and percentage change from baseline on Day 6 for 1) oxygenation parameter of P(A-a)O_2 gradient; 2) pathological oxygenation parameter of P(A-a)O_2 gradient; 3) ratio of $\text{PaO}_2/\text{FiO}_2$; 4) ratio of $\text{SpO}_2/\text{FiO}_2$. Percentage change from baseline of P(A-a)O_2 gradient and ratio of $\text{PaO}_2/\text{FiO}_2$ on Day 6 and follow-up will be summarized.

Reasons of missing AA gradient values on Day 6 will also be summarized.

The normal value of AA gradient for room air is calculated as: $2.5 + (0.21 \times \text{Age})$. All the results including change from baseline, and maximum change from baseline after 5 day intervention with sargramostim, normal AA gradient value for room air and flag of abnormality on Day 6 will be listed.

At least 25% reduction from baseline, at least 33% reduction from baseline, and at least 50% reduction from baseline in P(A-a)O_2 gradient and pathological gradient on Day 6 will be summarized for mITT population.

Survival status will be collected up to follow-up period (20 weeks after day 1). Death is considered as an event. All the mortality events and cause of death will be listed by treatment group and by patient. Number of patients died and survival time will be summarized by treatment group. Survival time will also be listed by patient. Risk and risk difference of all causes mortality by Day 28 and during the study period will also be summarized.

The hazard ratio will be estimated by the Cox proportional hazards model with treatment group as a covariate in the model. Relevant hazard rates, hazard ratio between treatment groups and associated p-values will be tabulated.

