6.1. Inclusion Criteria

The following patients will be enrolled

Recent (≤ 2 weeks prior to randomization) - Confident COVID-19 diagnosis confirmed by antigen detection test and/or PCR and/or positive serology, or any emerging and validated diagnostic laboratory test for COVID-19 within this period.

-In some patients, it may be impossible to get a confident laboratory confirmation of COVID-19 diagnosis after 24h of hospital admission because viral load is low and/or problems with diagnostic sensitivity. In those cases, in absence of an alternative diagnosis, and with highly suspect bilateral ground glass opacities on recent (< 24 h) chest-CT scan (confirmed by a radiologist and pulmonary physician as probable COVID-19), a patient can be enrolled as probable COVID-19 infected. In all cases, this needs confirmation by later seroconversion.

-Presence of acute hypoxic respiratory failure defined as (either or both)
saturation below 93% on minimal 2 l/min O₂
PaO₂/FiO₂ below 350

-Admitted to specialized COVID-19 ward

-Age 18-80

-Male or Female

-Willing to provide informed consent

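### Section 12.2 drops negative P(A-a)O2 gradient values from the primary analysis, which deletes favourable recorded outcomes in one direction only

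*Protocol*

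**What the plan says.** Sections 4.1 and 12.2 make the P(A-a)O2 gradient one component of the primary endpoint, beside PaO2/FiO2 and (in 12.2) SpO2/FiO2. Section 12.2 computes it from FiO2, "Atmospheric Pressure", water vapour pressure, PaCO2 divided by a fixed 0.8, and PaO2. It then states that a negative P(A-a)O2 "gradient would be removed from the primary analysis".

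On timing and testing, the same section says "Day 6 is the primary analysis point". For patients who leave earlier, "oxygenation at day of discharge will be used as value for measuring primary endpoint". For the comparison, "The difference of change from baseline between two groups will be tested by a t-test". The responder summary reads "At least 25% reduction from baseline, at least 33% reduction from baseline, and at least 50% reduction from baseline in" the gradient and the pathological gradient, for the mITT population.

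The only related provision is "Reasons of missing AA gradient values on Day 6 will also be summarized". The protocol describes no analysis that keeps the negative values. This is a rule that the protocol states, not a detail left to the SAP.

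**The concern.** The rule decides whether a value is analysed by looking at the value itself, after randomisation, and only at the favourable end. If sargramostim lowers the gradient, the active arm has more values near zero. More of them then fall below zero by error and are deleted. The active mean among the values that remain is pushed up by more than the control mean, and the estimated benefit shrinks.

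A patient with a positive baseline and a negative Day 6 gradient has a reduction above 100%, and so is a certain responder at all three cut-offs. If the removal carries over to the responder summary, such patients leave it. With 40 patients per arm there is little room for an avoidable loss of effect.

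**Working it through.** The protocol gives no share of negative values and no figure for the effect of this rule, so there is no stated result to reproduce. The steps below use its formulas, with assumptions marked.

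**1. When the gradient is negative.** Section 12.2 gives no pressure values; 760 and 47 mmHg are assumed, so the difference is 713.
- Room air, PaCO2 40: alveolar pressure = 0.21 × 713 − 40/0.8 = 99.7. The gradient is negative only if PaO2 exceeds 99.7, a PaO2/FiO2 above 99.7/0.21 = 475. At PaCO2 35 the limit is 505.
- FiO2 0.24, PaCO2 40: 0.24 × 713 − 50 = 121.1, a PaO2/FiO2 above 505.
- Entry (section 6.1) needs "PaO₂/FiO₂ below 350" and/or saturation below 93% on at least 2 l/min oxygen. At a ratio of exactly 350 on room air, PaO2 is 73.5 and the gradient is 99.7 − 73.5 = +26.2 (+32.5 at PaCO2 35, +20.0 at PaCO2 45).

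Negative baselines are therefore close to impossible, and the rule acts on Day 6 or discharge values.

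**2. What a negative value means.** Section 12.2 gives the normal room-air gradient as 2.5 + 0.21 × age: 6.3 at 18, 15.1 at 60, 19.3 at 80. A fully recovered patient is expected above zero, so a negative value mostly signals error. One step of the FiO2 table in section 9.2, 24% to 28%, moves the gradient by 0.04 × 713 = 28.5 mmHg. Under-estimating FiO2 by that step turns any true gradient below 28.5 negative, and it is deleted. The same error at a higher true gradient stays in, and so does the same step upward in any patient.

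**3. Size of the bias.** Assumed Day 6 means are 25 (active) and 40 (control), SD 25, true difference 15.

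*Day 6 mean, normal model.* The mean of the values kept is μ + σ·φ(μ/σ)/Φ(μ/σ).
- Active: 25 + 7.19 = 32.2, with 15.9% removed.
- Control: 40 + 2.93 = 42.9, with 5.5% removed.
- Difference 10.7; loss 4.3/15 = 28%.

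*Change from baseline, normal model.* With equal SDs and correlation ρ, the baseline mean of those kept also rises, by ρ times the Day 6 shift. The loss is (1 − ρ) × (7.19 − 2.93) = (1 − ρ) × 4.26.
- ρ = 0.3: loss 2.98, difference 12.0, 20% lost.
- ρ = 0.6: loss 1.70, difference 13.3, 11% lost.

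*Day 6 mean, skewed model.* The true gradient is lognormal (always positive) plus normal measurement error, with the same means and SD.
- Error SD 5: about 3% vs 0.1% removed, about 5% of the effect lost.
- Error SD 10: about 8-9% vs 1-2% removed, about 15% lost.

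*Planning SD from section 12.1.* SD is 10, and the 10% improvement is read as 10 units (an assumption). The stated power of 0.90 is not reproduced: 40 per arm at two-sided 0.01 gives 0.97. That is a separate matter. Using the change-from-baseline formula above with ρ from 0.3 to 0.6:

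| Assumed control Day 6 mean | Removed, active vs control | Expected difference (true 10) |
|---|---|---|
| 30 | 2.3% vs 0.1% | 9.6-9.8 |
| 20 | 15.9% vs 2.3% | 8.4-9.1 |
| 15 | 30.9% vs 6.7% | 7.4-8.5 |

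In the first row 2.3% of 40 is about one patient, and 2-4% of the effect is lost.

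**4. Responders.** As an illustration, 24/40 vs 16/40 is a difference of 20.0 points. If 4 active and 1 control responders are removed for negative values, it becomes 20/36 vs 15/39, or 55.6% − 38.5% = 17.1 points.

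**5. No treatment effect.** With the same outcome distribution in both arms, the same share is removed and both means shift equally. The expected difference stays zero.

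**The case against.** The best defence is data quality. A negative gradient is physically implausible, and leaving implausible values out has a rationale. That is right about the single value, and it defeats the tempting reading that the rule deletes the truly best-oxygenated patients. Those removed have the best oxygenation as recorded, which is not proof that it was truly best. It does not rescue the rule, because error takes a value below zero mainly when the true gradient is already low. Deletion still follows outcome, and no source check is required.

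Four further readings go beyond the documents.
- *A large bias.* The 28% applies to the Day 6 mean under a normal model that puts 16% of the active arm below zero. Section 12.2 tests change from baseline, where the same case gives 11-20%. A skewed model gives about 5-15% on the Day 6 mean.
- *The whole primary comparison is lost.* The sentence removes gradient values, not patients. Nothing takes these patients out of PaO2/FiO2 or SpO2/FiO2.
- *Responders are certainly lost.* Section 12.2 summarises responders for the mITT population without repeating the removal, and promises all available efficacy data for that population. Their loss is possible but not stated.
- *A false-positive risk.* Equal outcome distributions give no expected bias, and a real benefit is shrunk.

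**Conclusion.** The rule is wrong as written, for the gradient component only. It deletes outcomes by their value, in the favourable direction, and no other provision restores them; summarising the reasons for missing Day 6 values does not. If treatment works, the gradient comparison is biased toward no effect.

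The size cannot be fixed from the protocol, because it depends on the share of negative values. At 1-2% it is negligible. In the assumed case of 25 vs 40 with SD 25, a loss of about 11-20% on the tested quantity is a fair working range for correlations of 0.3-0.6 under a normal model. It would be smaller if the true gradients are skewed and the measurement error modest. These figures also rest on 760 and 47 mmHg. The point should be fixed, but it does not by itself invalidate the primary analysis.

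**What to change.** Replace the sentence in section 12.2, and any matching sentence in the SAP, with:

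> Negative gradients are checked against source (FiO2, PaCO2, PaO2, entry errors) without knowledge of arm. Unresolved values stay in the primary analysis, as measured or set to zero by one pre-specified rule, and count as responders at all cut-offs. Analysis without negative values is a sensitivity analysis, with counts by arm.

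Either way of keeping the values avoids the deletion; what matters is that one is chosen in advance. Because the trial is open label, the person who checks the values should work from listings without the arm. The cost is one sentence and one sensitivity table, with no new data.
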